11.10.2.2.2. Statistical analysis of pharmacokinetic parameters

Plasma concentration-time data will be listed by dose, age group, and summarized using descriptive statistics (n, mean, SD, median, minimum and maximum) by planned relative assessment time. Mean and/ or median values will be plotted over time. Individual plasma and urinary (if available) pharmacokinetic parameter values as well as a descriptive summary (mean, standard deviation, median, minimum, maximum, geometric mean, and the standard deviation, coefficient of variance percent (CV%) and 95% confidence interval of log-transformed parameters [if applicable]) by dose cohort will be reported.

Cmax and AUC (AUC($0-\infty$), single dose, and AUC($0-\tau$), steady state) will be plotted as a function of the dose administered. If more than 2 dose cohorts are required to reach MTD (or the recommended dose based on available safety, PK and response data), dose proportionality of AUC and Cmax for GSK3326595 following single dose administration and AUC($0-\tau$) and Cmax following repeat dose administration will be assessed graphically and using the power model as described below:

 $\log (\text{pharmacokinetic parameter}) = a + b * \log(\text{dose})$

where a is the intercept and b is the slope.

The power model will be fitted by restricted maximum likelihood (REML) using Statistical analysis system (SAS) Proc Mixed. Both the intercept and slope will be fitted as fixed effects. If there is sufficient data, the model may also be fit with the intercept and/or slope as random effects depending on the ability of the model to converge and on estimation of variance-covariance matrix. The mean slope and corresponding 90% confidence interval will be estimated from the power model.

11.10.2.2.3. Food Effect and Relative Bioavailability Sub-Study

Pharmacokinetic (PK) parameters AUC($0-\infty$), and Cmax will be log-transformed and analyzed separately using a mixed-effects model with fixed-effect term for fed status (fed or fasted)/formulation (tablet or capsule), and subject as a random effect. Point estimates and their associated 90% CIs will be constructed for the differences between fed and in fasted state, between tablet and capsule. For the relative bioavailability analysis, tablets are the test formulation and capsules are the reference. The point estimates and their associated 90% CIs were then back transformed to provide point estimates and 90% CIs for the ratios of fed/fasted and tablet/capsule. Non-parametric methods such as the Hodges and Lehmann estimator will be used to estimate the median differences between

the fed treatments and the fasted state treatments for tmax and $t^{1/2}$. An associated 90% CI for the median differences will be constructed.

Based on the US FDA guidance on food-effect bioavailability studies, the absence of a food-effect will be established if the 90% CI of the ratio for Cmax and AUC, based on log-transformed data, is within the 80 to 125% equivalence limit. Recommendation on the clinical significance of the effect of food will be based on the magnitude of the change and our understanding of the exposure-clinical response relationship.

For the evaluation of food effect, tmax at fed and fasted status will be presented by subject and dose cohort in tabular and graphical form.

11.10.2.3. Efficacy Analysis

The confirmed overall response rate (ORR) is defined as the percentage of subjects with a confirmed complete response (CR) or a partial response (PR) at any time as per disease-specific criteria (Section 14.4). Subjects with unknown or missing response will be treated as non-responders, i.e. these subjects will be included in the denominator when calculating the percentage. Exact methods for calculated confidence intervals will be given in the RAP.

The number and types of responses, as outlined in RECIST 1.1 (for subjects with solid tumors), RANO (for subjects with GBM), and Lugano (for subjects with NHL), will be listed and summarized separately, as appropriate.

The observed confirmed ORR will be reported at the interim and final analysis for each cohort specified in Part 2 treated at RP2D. The estimates along with 95% confidence interval (CI) based on a normal approximation will be provided. Bayesian inference based on summary statistics from the posterior distributions of each ORR will be reported at interim and final analyses. The posterior mean and posterior 2.5% and 97.5% percentiles of the ORR will be calculated for each cohort. In addition, the posterior probability that the ORR exceeds its corresponding historical control will be reported for each cohort.

Progression-free survival rate (PFSR) is calculated from the start of treatment until the date of progression or death from any cause. The PFSRs at 6 months were estimated by the Kaplan-Meier method. These rates estimated the proportion of patients who did not progress and were alive at month 6. The 95% confidence intervals for the PFSR at month 6 will be estimated using Greenwood's estimate of the standard error (SE) and a linear transformation of the progression-free survival function.

Duration of response is defined as the time from first documented evidence of CR or PR until the first documented sign of disease progression or death, for the subset of subjects with a confirmed CR or PR. Duration of response will be summarized descriptively for each cohort, if data warrant, using Kaplan-Meier medians and quartiles. Details on rules for censoring will be provided in the RAP.

For the ACC tablet cohort, duration of response will be analyzed as determined by the Investigator assessment.

For the analysis of Progression-free survival (PFS), if the subject received subsequent anti-cancer therapy prior to the date of documented events, PFS will be censored at the last adequate assessment (e.g. assessment where visit level response is CR, PR, or stable disease [SD]) prior to the initiation of therapy. Progressive disease (PD) will also be defined per standard criteria. Otherwise, if the subject does not have a documented date of events, PFS will be censored at the date of the last adequate assessment. Further details on rules for censoring will be provided in the RAP. PFS will be summarized by cohort specified in Part 2, if data warrant, using Kaplan-Meier quantile estimates along with 2-sided 95% CIs at the time of final analysis.

For the analysis of overall survival (OS), the last date of known contact will be used for those subjects who have not died at the time of analysis; such subjects will be considered censored. Further details on rules for censoring will be provided in the RAP. OS will be summarized by cohort specified in Part 2, if data warrant, using Kaplan-Meier quantile estimates along with 2-sided 95% CIs at the time of final analysis.

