11.6. Bayesian Predictive Adaptive Design for ER+BC Cohort

The ER+BC cohort will employ the Bayesian design that allows the trial to be monitored frequently with the constraint of both Type I and Type II error rates. The evaluation is designed to exclude a 10% overall response rate (ORR) representing best available therapy in favour of a 25% ORR. A close to non-informative prior will be used. Let p denote the response rate, the prior distribution used is $p \sim Beta$ (0.025, 0.075). The cohort will be stopped early due to futility if the predictive probability of success is less than

8%. The success is defined as posterior probability of ORR > 10% at the end of the cohort is larger than 80%. The first interim analysis will be performed when at least 10 subjects become evaluable. The max sample size is 35 subjects, and the design will have type I error of 0.10 and power of 82%.

The decision rules, specifying the number of subjects with a clinical response needed for continuing enrolment or, stopping for futility, are displayed in Table 19. The methodology is based on the predictive probability of success if enrolment continues to maximum number of subjects [Lee, 2008]. The interim analysis will be for futility only, i.e., the dose expansion cohort will not stop early for efficacy.

Number of Evaluable Subjects	≤ This Number of Confirmed Responses to Stop Early for Futility	Probability of continuing enrolling when ORR=0.1	Probability of continuing enrolling when ORR=0.25
10	0	0.6513	0.9437
11	0	0.6513	0.9437
12	0	0.6513	0.9437
13	0	0.6513	0.9437
14	1	0.3971	0.8843
15	1	0.3971	0.8843
16	1	0.3971	0.8843
17	1	0.3971	0.8843
18	1	0.3971	0.8843
19	1	0.3971	0.8843
20	1	0.3971	0.8843
21	1	0.3971	0.8843
22	2	0.2938	0.8674
23	2	0.2938	0.8674
24	2	0.2938	0.8674
25	2	0.2938	0.8674
26	2	0.2938	0.8674
27	3	0.2108	0.8511
28	3	0.2108	0.8511
29	3	0.2108	0.8511
30	3	0.2108	0.8511
31	3	0.2108	0.8511
32	4	0.1509	0.8369
33	4	0.1509	0.8369
34	4	0 1509	0.8369

Table 19Decision Making Criteria for ER+BC Futility

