1. INTRODUCTION

This reporting and analysis plan (RAP) details all planned analyses required for a Clinical Study Report of study 204653.

The RAP was written by staff of ICON Clinical Research. The execution of primary and secondary analyses of the RAP, with exception to mTPI analysis and Part 2 Bayesian hierarchical design analysis, will be undertaken by staff of ICON Clinical Research. Additional interim and ad hoc analyses are also described within this document.

In addition, pharmacodynamic/ biomarker analysis and translational research analysis maybe identified and addressed in a separate RAP, if applicable. Exploratory analyses may be conducted at a later time.

All decisions regarding final analysis, as defined in this RAP document, have been made prior to database freeze of the study data.

1.1. Revision Chronology:

Version	Date	Revision Description
1.0	8 Sep 2022	Original
1.1	12 Sep 2022	 Section 4.1: Removed stray bullet in Table 7. Section 6.3: Corrected reference in to Section 4.2 (not 4.1). Section 7.2.6: Updated description of TTR endpoint in Section 7.2.6 from time-to- event to continuous variable Section 15.12.12: Updated example shell for Listing 55 to "custom per GSK".
1.2	21 Sep 2022	 Section 7.2.4: Added the survival estimates to be presented and the method for calculating 95% CI, as it differs from the estimates in Section 7.1.3. Section 7.27: Added the estimates presented and method for calculating 95% CI.
1.3	30 Sep 2022	 Figure 4.5 should be linear not log-transformed parameters. Added Section 3.1.3 to account for interim analysis that used evaluable population on Part 1 subjects. Added evaluable population definition for Part 1 subjects for interim analysis.
1.4	18 Oct 2022	 Added hyperlinks within the text. Added "number of infusions" to Section 8.1.1.1. Added "calcium corrected" to list of chemistry measures in Section 8.4.1. Updated titles for Table 3.21, Table 3.65, Table 4.5, Figures 4.6, Listing 14, Listing 79, Listing 82, and programming notes for Table 4.5 Table 4.7 and Figure 4.1 Figure 4.4 in Section 15.12. Added more text to Section 8.4.6, and hepatobiliary injury definition. Removed Figure 4.5 per GSK. Added number category definitions for SBP and DBP in Section 15.8.3.
1.5	10 Nov 2022	 Corrected template references for Table 3.48 and Table 3.50 in Section 15.12. Corrected subgroup for Listing 29 which should be ACC only.
1.6	18 Nov 2022	Update Listing 77 and 78 titles to match previous delivery.

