7.1. Primary Efficacy Analyses

7.1.1. Confirmed Overall Response Rate (ORR) based on RECIST 1.1 for Part 2 (non-GBM, non-NHL) cohorts

The primary endpoint for all Part 2 cohorts, except GBM, will be overall response rate (ORR). The timepoint overall response is assessed by the investigator and recorded on the eCRF. The ORR endpoint is defined as % of subjects achieving a best response of CR and PR recorded from the start of treatment until disease progression or start of new anti-cancer therapy, whichever is earlier.

Best response will be determined programmatically based on investigator assessment at each time point. If there are two assessments, separated by not evaluable (NE) assessment(s), the best response shall be assessed applying the algorithm below, collapsing data by ignoring NE assessments. The first assessment may occur before the first planned assessment.

Confirmed responses, as outlined in RECIST 1.1 [Eisenhauer, 2009] will be summarized, as appropriate. Confirmation of response may be based on planned and/or unscheduled assessments.

The confirmed overall response rate (ORR) is defined as the ORR as per disease-specific criteria (more details in protocol Section 14.4). Subjects with unknown or missing response will be treated as non-responders, i.e., these subjects will be included in the denominator when calculating the percentage. The best overall response is a subject's best response over the time period referenced. In addition, with respect to best response:

- To be assigned a status of SD, follow-up disease assessment must have met the SD criteria at least once after the first dose for a minimum of 49 days.
- If the minimum time for SD is not met, best response will depend on the subsequent assessments. For example, if an assessment of PD follows the assessment of SD and SD does not meet the minimum time requirement the best response will be PD. Alternatively, subjects lost to follow-up after an SD assessment, not meeting the minimum time criteria, will be considered not evaluable.
- To be assigned a status of PR or CR, a confirmatory disease assessment should be performed no less than 4 weeks (28 days) after the criteria for response are first met.

The ORR will be summarized with a 2-sided 95% exact confidence interval based on the Clopper-Pearson method. The observed confirmed ORR will be reported at the interim and final analysis and will be summarized by cohort.

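### For ER+BC and HPV+, the SAP's final analysis omits the posterior probability that defines success, and SAP 2.1 does not declare the omission

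*Protocol*

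**What the plan says.** **Protocol.** Section 11.10.2.3 says that "Bayesian inference based on summary statistics from the posterior distributions of each ORR will be reported at interim and final analyses". It lists the posterior mean and the 2.5% and 97.5% points, and then says that "the posterior probability that the ORR exceeds its corresponding historical control will be reported for each cohort".

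For two cohorts this probability decides success. For ER+BC (section 11.6), "The success is defined as posterior probability of ORR > 10% at the end of the cohort is larger than 80" per cent, with a Beta(0.025, 0.075) prior and at most 35 subjects. For HPV+ (section 11.7) the threshold is 87.6%, with a Beta(0.03, 0.07) prior and at most 28 subjects. Both are stand-alone beta-binomial designs.

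**SAP.** Sections 3.1.5 and 3.1.6 repeat these priors and thresholds under interim-analysis headings. Section 7.1.1, the primary efficacy analysis for these cohorts, says: "The ORR will be summarized with a 2-sided 95% exact confidence interval based on the Clopper-Pearson method". Table 2.1 in Appendix 12 matches it: best response with confirmation and an exact interval. No posterior quantity appears in Section 7 or among the efficacy tables and figures.

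SAP Section 1 assigns the primary and secondary analyses to the contract research organisation "with exception to mTPI analysis and Part 2 Bayesian hierarchical design analysis". That exception does not reach ER+BC or HPV+. SAP 2.1 states that nothing departs from Amendment 8, and its list of exceptions does not mention posterior output.

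**The concern.** The protocol asks of each cohort whether a posterior probability passed a fixed threshold. For ER+BC and HPV+, no planned final display computes that probability or states the answer. Two things follow.

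First, someone with only the planned table may use the interval as a stand-in and ask whether it excludes 10%. That is a much stricter test than the one the cohorts were designed around.

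Second, the success counts implied by the design hold only at 35 and 28 subjects. Amendment 8 stopped recruitment, and SAP 3.1.7 records that NSCLC had not reached 10 subjects at that point, so a Part 2 cohort ending short is not far-fetched. At any other n the count has to be worked out again from the posterior.

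**Working it through.** **Formula.** With prior Beta(a, b) and x responders among n, the posterior is Beta(a + x, b + n − x). Success is judged on P(ORR > 0.10) = 1 − BetaCDF(0.10; a + x, b + n − x).

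**Reproducing the plan's figures.**

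- ER+BC at n = 35: x = 5 gives 1 − BetaCDF(0.10; 5.025, 30.075) = 0.753, and x = 6 gives 1 − BetaCDF(0.10; 6.025, 29.075) = 0.883. The rule is therefore at least 6/35. Predictive-probability futility bounds at the 8% cut-off match protocol Table 19 at every n. An exact binomial recursion through them gives type I error 0.0984 and power 0.8153, against 0.10 and 82% stated.
- HPV+ at n = 28: x = 5 gives 1 − BetaCDF(0.10; 5.03, 23.07) = 0.8753, just under 0.876, and x = 6 gives 1 − BetaCDF(0.10; 6.03, 22.07) = 0.954. The rule is at least 6/28. Bounds at the 1% cut-off match Table 20 at every n. Type I error is 0.0517 and power 0.8702, against 0.05 and 87% stated.

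The 5/28 case shows that the call cannot be made by eye.

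**Success call beside the SAP's interval.**

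| Cohort | Result | P(ORR > 10%) | Success | Clopper-Pearson 95% | Includes 10% |
|---|---|---|---|---|---|
| ER+BC | 6/35 | 0.883 | yes | 6.6% to 33.6% | yes |
| ER+BC | 7/35 | 0.952 | yes | 8.4% to 36.9% | yes |
| ER+BC | 8/35 | 0.983 | yes | 10.4% to 40.1% | no |
| HPV+ | 6/28 | 0.954 | yes | 8.3% to 41.0% | yes |
| HPV+ | 7/28 | 0.986 | yes | 10.7% to 44.9% | no |

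**Is the exact method the cause?** No. At 6/35 the normal-approximation interval named in protocol 11.10.2.3 is 0.171 ± 1.96 × 0.0637, or 4.7% to 29.6%, and the posterior 2.5% and 97.5% points are 6.8% and 31.1%. At 6/28 the two intervals are 6.2% to 36.6% and 8.7% to 38.1%. All include 10%. A two-sided 95% interval leaves 2.5% in the lower tail, while the success rules tolerate up to 20% or 12.4% there.

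**How often the two would differ at full enrolment.** This is P(success) minus P(interval excludes 10%), with futility stopping included.

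- ER+BC: 0.8153 − 0.6453 = 17.0% at a true ORR of 25%; 0.0984 − 0.0182 = 8.0% at 10%.
- HPV+: 0.8702 − 0.7708 = 9.9% at a true ORR of 30%; 0.0517 − 0.0174 = 3.4% at 10%.

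Reading the interval as the verdict would thus take power from 82% to 64.5% in ER+BC and from 87% to 77.1% in HPV+.

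**A cohort that ends short (illustration only).** The documents do not give the attained n, so n = 20 is an assumption. For ER+BC, 3/20 gives 1 − BetaCDF(0.10; 3.025, 17.075) = 0.709, and 4/20 gives 1 − BetaCDF(0.10; 4.025, 16.075) = 0.886. The threshold is met at 4 responders, not 6. Ignoring the futility looks, P(at least 4 of 20) at ORR 10% is 1 − BinomCDF(3; 20, 0.10) = 0.133, so the stated type I error of 0.10 does not carry over.

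**The case against.** **The verdict can be recovered.** Priors and thresholds stand in SAP 3.1.5 and 3.1.6, and Table 2.1 gives responders and n, so anyone can compute the posterior. This stands, and it limits the harm: what is missing is an unprinted number and an undeclared departure. The protocol nevertheless promises that the number will be reported, and it is the primary success criterion.

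**The interval does not contradict the rule.** A reader might infer from 6/35 and 6/28 that the SAP's interval and the protocol's success rule conflict. The documents do not support that. Neither makes the interval a decision rule, and the credible interval that the protocol itself promises includes 10% as well.

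**The gap does not cover every Bayesian cohort.** A reader might infer that the SAP drops all posterior output. It does not. SAP 3.1.2 says that final evaluations for mTCC, TNBC and both NHL cohorts use the hierarchical model, and that P(π_j > C_j) will be computed. Section 1 only moves that work away from the contract research organisation. What is missing there is a named place of reporting. GBM does not belong to the point either: its final criterion is a count (at least 8 of 28), its SAP output is a Kaplan-Meier rate, and the promise in protocol 11.10.2.3 concerns ORR.

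**Conclusion.** The point holds for ER+BC and HPV+. The SAP's final analysis leaves out the posterior summaries promised in protocol 11.10.2.3, including the probability that defines success, and SAP 2.1 does not say so. This should be corrected, but it does not bias any planned estimate.

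Its size is the risk that the interval is taken for the verdict: at full enrolment the two readings differ with probability 17.0% (ER+BC, true ORR 25%) and 9.9% (HPV+, true ORR 30%). These figures assume the stated priors, enrolment to 35 and 28 unless stopped for futility, and futility bounds applied at every n as in Tables 19 and 20. The n = 20 case shows only that the success count changes with n; it says nothing about actual enrolment.

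SAP Section 3.2 is withheld in the public copy, so the finding rests on the visible text. The efficacy tables and figures in Appendix 12 are numbered without a gap from 2.1 to 2.23, and none shows a posterior quantity.

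**What to change.** 1. **ER+BC and HPV+.** Add to SAP 7.1.1 and to the display list the posterior mean, the 2.5% and 97.5% points, P(ORR > 10%) at the attained n, the threshold (80% or 87.6%) and the success call, using Beta(0.025, 0.075) and Beta(0.03, 0.07). Footnote that the stated type I error and power apply only at the planned maximum n, and that the 95% interval is descriptive.
2. **TNBC, mTCC and both NHL cohorts.** State where the final hierarchical posterior planned in SAP 3.1.2 will be reported. No new analysis is needed.
3. **ACC capsule, ACC tablet and NSCLC.** These are Simon designs with no stated prior. Record in SAP 2.1 that the posterior output of protocol 11.10.2.3 is not produced for them.

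The cost is one short closed-form table for two cohorts and a few sentences. No new data are needed, and no existing display changes.

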11.10.3. Other Analyses

11.10.4. Simulations and Design Operating Characteristics

11.10.4.1. Simulation Description

Extensive simulations have been conducted to develop and understand the performance of the adaptive design; the hierarchical model including clustering mechanism, interim monitoring, and decision criteria.

11.10.4.2. Software Details

Simulations were conducted by the software provided by Berry Consultants. For each assumed scenario, 500 sets of trials were simulated. Posterior distributions were estimated via Markov chain Monte Carlo methods using 50,000 iterations for each analysis, discarding the first 2,000 iterations for each analysis as burn-in.

11.10.4.3. Trial Sample Size and Simulation Scenarios

Sample size requirements for halting enrollment at interim analyses for simulations is based on the number of subjects enrolled; while in practice, they will be based on the number of subjects with available response data. This discrepancy is due to software feasibility but should not have a significant impact on operating characteristics of the design. Simulations assumed interim analyses occurred every 4 weeks, with the first interim analysis occurring once 40 subjects have been enrolled. The time from subject entry until the response assessment was performed is assumed to be 24 weeks. The maximum length of time for each study is 120 weeks ± 6 weeks (roughly 2.5 years).

Although actual enrollment may vary, predicted enrollment during a 2-year time period is incorporated into the simulations. Cohort, projected enrollment and the historical control and clinically meaningful response rates used in simulations are shown in Table 21.

	Cohorts						
	TNBC	mTCC	NHL[+]	NHL[-]			
Project Enrollment in	32	40	25	25			
2-year time period; n							
Max Sample size; n	32	40	25	25			
Scenarios							
All Null	10%	15%	10%	10%			
All Positive	25%	30%	30%	30%			
All Moderate	20%	20%	20%	20%			
2 Null, 2 Positive	25%	15%	30%	10%			
3 Null, 1 Positive	10%	15%	30%	10%			
Proportion of Trials that I	Proportion of Trials that Declare each Cohort Efficacious (Measure of Power or Type I Error						
Rate)							
All Null	0.05	0.10	0.06	0.05			
All Positive	0.92	0.88	0.95	0.96			
All Moderate	0.67	0.39	0.58	0.57			

Table 21Simulation Scenarios and Design Characteristics

		Coh	orts			
	TNBC	mTCC	NHL[+]	NHL[-]		
2 Null, 2 Positive	0.82	0.12	0.87	0.13		
3 Null, 1 Positive	0.09	0.10	0.81	0.11		
Proportion of Trials that I	Declares Early Fut	tility				
All Null	0.50	0.52	0.47	0.42		
All Positive	0.03	0.05	0.02	0.01		
All Moderate	0.09	0.22	0.06	0.08		
2 Null, 2 Positive	0.09	0.41	0.04	0.24		
3 Null, 1 Positive	0.39	0.45	0.06	0.31		
Proportion of Trials that Pick all the Positive Cohorts						
All Null	N/A					
All Positive	0.76					
All Moderate	N/A					
2 Null, 2 Positive	0.74					
3 Null, 1 Positive	0.81					

Due to the 'borrowing' nature of the model, the design is evaluated across a variety of scenarios for the distribution of true ORRs across the four cohorts. These are shown in Table 21.

The "All Positive" scenario assumes all cohorts are responsive at the defined clinically meaningful RR levels. The "Null" case assumes all cohorts are nonresponsive at the historical control RRs. The "All Moderate" scenario assumes all cohorts show moderate RR levels in between the historical control and clinically meaningful RR levels. The other three scenarios consider various situations where cohorts are either responsive (at the clinically meaningful RR level) or not (at the historical control RR level).

